5.4.2 Prohibited Concomitant Medications

The following treatments are prohibited while in this study:

• No other investigational therapy should be given to patients. No anticancer agents other than the study treatments should be given to patients. If such agents are required for a patient, then the patient must first be withdrawn from the study.

CONFIDENTIAL

Sponsor/Development Innovations Study Numbers: AC699-001/BRE 401

Final Protocol: 07 May 2024 Version 4.0

- Anticoagulation with coumarin-derivatives is not permitted. However, the use of anticoagulants to keep the port line patent will be permitted. Should a thrombotic event occur while the patient is in the study and receives anticoagulant treatment, and the patient remains in the study, oral Xa inhibitors will be the preferred anticoagulant treatment.
- Proton pump inhibitors are prohibited due to their long PD effect. This type of drugs should be replaced with H2-antagonists or antacids.
- Any new or concomitant QT prolonging medications within the last 6 months.

6.1 Dose Modifications Due to Hematologic Toxicity

Dose modifications due to hematologic toxicity are described in Table 3.

CONFIDENTIAL

Sponsor/Development Innovations Study Numbers: AC699-001/BRE 401

Final Protocol: 07 May 2024 Version 4.0

Table 3 Dose Modifications Due to Hematologic Toxicities

Event	AC699 Dose ^a	
Neutropenia (ANC)		
ANC <1.0 -0.5 × 10 ⁹ /L (Grade 3)	Closely monitor patient, diagnose the cause, and treat accordingly	
	If not recovered in 2 weeks: hold drug	
	- if it recovers to \leq Grade 2, restart at the same dose.	
	- if within 3 weeks of drug hold it does not recover to \leq Grade 2, resume dose at one lower dose level.	
ANC <0.5 × 10 ⁹ /L (Grade 4)	Hold dose until recovery to \leq Grade 2 (ANC \geq 1.0 \times 10 ⁹ /L) ^b ,	
	• If resolved in ≤7 days, then resume without a dose reduction.	
	• If resolved in >7 days but <2 weeks, then resume dose at one lower dose level.	
Recurrence of ANC $<0.5 \times 10^9/L$ (Grade 4)	Hold dose until recovery to \leq Grade 2 (ANC \geq 1.0 \times 10 ⁹ /L), then resume at 1 lower dose level ^b .	
Thrombocytopenia		
Platelets $<50 \times 10^9/L$ (Grade 3)	Hold dose until improvement to \leq Grade 2 (platelets $<$ 75-50 \times 10 9 /L b)	
	• If resolved in ≤7 days, then resume without a dose reduction and monitor platelets count.	
	• If resolved in >7 days but <2 weeks, then resume dose at 1 lower dose level.	
Other hematologic events		
Other severe and non-life- threatening hematologic toxicities (\geq Grade 3)	Hold or maintain dose at the treating physician's discretion.	
toricines (=Orace 3)	Monitor at least weekly and manage accordingly.	

^a Any patients who require a treatment delay of more than 3 weeks due to treatment-related toxicity will be discontinued from study treatment unless the treating physician and the Medical Monitor agree that continued treatment at lower doses is in the best interest of the patient.

Re-treatment criteria = ANC recovery $\ge 1.0 \times 10^9 / L$ and platelets $\ge 75 \times 10^9 / L$.

ANC = absolute neutrophil count

CONFIDENTIAL

Study Drug: AC699 Sponsor/Development Innovations Study Numbers: AC699-001/BRE 401

Hold AC699 treatment; perform at least weekly complete blood count (CBC) with differentials until toxicity resolves (ANC recovery $\ge 1.0 \times 109$ /L and platelets $\ge 75 \times 109$ /L).

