A cumulative incidence of any of the following treatment-related events will trigger a hold on further patient enrollment for all dose cohorts until the SRC determines if it is safe to continue:

- Grade 4 adverse events (AEs) > 25%,
- Serious adverse events (SAEs) > 25%,
- AEs leading to discontinuation from study > 25%,
- Grade 5 AEs > 10%.

The 3+3 dose-escalation procedure is shown in Table 2.

CONFIDENTIAL

Study Drug: AC699 Sponsor/Development Innovations Study Numbers: AC699-001/BRE 401

Table 2 Dose-Escalation (3+3) Design

Number of Patients with a DLT	Action
0 of 3 patients	Escalate to next dose level
1 of 3 patients	Accrue additional evaluable patients at the current dose level (for a total of up to 6 evaluable patients) ^a
1 of 6 patients	Escalate to the next dose level
2 or more patients in a dose level group of up to 6 patients	The MTD has been exceeded

DLT = dose-limiting toxicity, MTD = maximum-tolerated dose

Dose-Limiting Toxicity

Toxicity will be assessed using the NCI CTCAE Version 5.0 unless otherwise specified. Dose-limiting toxicities thought to be related to AC699 during the DLT period (first 28 days) will be defined as any of the following toxicities if considered at least possibly related to study treatment, i.e., not attributable to the disease or disease-related process under investigation, or other non-study related explanation, and that means at least 1 of the hematologic or non-hematologic criteria below:

Dose-limiting toxicities (DLTs) will be defined as follows:

• Any Grade 5 toxicity

Hematological:

- o Grade 4 neutropenia for >7 days; or febrile neutropenia (ANC <1000/mm³ with a single temperature of >38.3° C [101° F] or a sustained temperature of ≥ 38° C [100.4° F] for more than 1 hour)
- o Grade 4 thrombocytopenia; or Grade 3 thrombocytopenia associated with clinically significant bleeding, including any bleeding that warrants a platelet transfusion
- o Grade 4 anemia (life-threatening consequences requiring urgent interventions)

• Non-hematological:

- o Grade 3 or 4 non-hematologic toxicity, with the **exception of**:
 - Alopecia;
 - Grade 3 nausea, vomiting, or diarrhea if well-controlled by supportive care within 72 hours;
 - Grade 3 skin rash that improves in ≤7 days, with or without supportive care;
 - Grade 3 fatigue that improves in ≤ 7 days, with or without supportive care;
 - Grade 3 endocrinopathies that only require treatment with hormone replacement therapy;

CONFIDENTIAL

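### After Cycle 1, Table 3 does not require an immediate hold of AC699 for febrile neutropenia at ANC 0.5 to <1.0 × 10⁹/L or for Grade 4 anemia

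*Protocol*

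**What the plan says.** Protocol Section 5.1 (Dose-Limiting Toxicity) lists the hematologic DLTs for the first 28 days. They include "or febrile neutropenia (ANC <1000/mm³ with a single temperature" above a stated limit, or a sustained fever, and "Grade 4 anemia (life-threatening consequences requiring urgent interventions").

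Protocol Section 6 refers toxicities of Grade 3 or higher to Tables 3 and 4. Table 3 in Section 6.1 covers hematologic toxicity and has five event rows:

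- **ANC 0.5 to <1.0 × 10⁹/L (Grade 3).** The first action is "Closely monitor patient, diagnose the cause, and treat accordingly". The hold comes second: "If not recovered in 2 weeks: hold drug".
- **ANC <0.5 × 10⁹/L, its recurrence, and platelets <50 × 10⁹/L** (three rows). Each requires a hold straight away. The footnote "Hold AC699 treatment; perform at least weekly complete blood count (CBC) with differentials until toxicity resolves" belongs to these rows.
- **The catch-all row**, headed "Other severe and non-life- threatening hematologic toxicities" of Grade 3 or higher. Its action begins "Hold or maintain dose at the treating physician" and leaves the choice to discretion, with at least weekly monitoring.

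Section 6 also has a rule for DLTs in Cycle 1: the patient can go on at the next lower dose once the toxicity has settled to Grade 1 or baseline. A general rule allows, but does not require, a delay of up to 3 weeks for adverse events.

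**The concern.** A dose-modification table tells the site what to do with the next tablet. Table 3 requires an immediate stop for low platelets even without bleeding. For two events that Section 5.1 treats as dose-limiting in the first 28 days, one of them described there as life-threatening, it does not. In one case it defers the hold by two weeks whether or not the patient is febrile. In the other it offers either no row or a discretionary one.

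What is at stake is the safety of the individual patient in later cycles. Scheduled hematology is then done only on Day 1 of each 28-day cycle (Schedule of Assessments; Section 7.3.2), and the Grade 3 ANC row asks for close monitoring without giving an interval.

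**Working it through.** No sample size, power or error rate is involved. The check maps each hematologic DLT in Section 5.1 to its row in Table 3.

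**Units.** Section 5.1 gives ANC per mm³ and Table 3 gives it per litre. 1000/mm³ × 10⁶ mm³/L = 1.0 × 10⁹/L. The febrile neutropenia definition therefore spans both the Grade 4 range (<0.5) and the Grade 3 range (0.5 to <1.0).

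**Mapping.**

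| Hematologic DLT (Section 5.1) | Row in Table 3 | Immediate hold required? |
|---|---|---|
| Grade 4 neutropenia for more than 7 days | ANC <0.5 | Yes |
| Grade 4 thrombocytopenia | Platelets <50 | Yes |
| Grade 3 thrombocytopenia with significant bleeding | Platelets <50 | Yes |
| Febrile neutropenia | ANC <0.5, or ANC 0.5 to <1.0 | Only if ANC <0.5 |
| Grade 4 anemia | None, or the catch-all | No |

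Count of events: 3 held + 1 held in part + 1 not held = 5. Count of rows: 3 with an immediate hold + 2 without = 5.

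**Length of the deferral in the Grade 3 ANC row.** Dosing is once daily (Synopsis). 2 weeks × 7 days × 1 dose per day = 14 doses, and 14/28 = half a cycle. This is the most that the row permits before the hold is compulsory. It does not estimate what would happen.

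**Does other text close the gap?**

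- *Cycle 1 DLT rule (Section 6).* Continuation depends on resolution, so an interruption is implied. The rule applies to Cycle 1 only.
- *General delay rule (Section 6).* It applies in every cycle but is permissive.
- *Re-treatment criterion under Table 3 (ANC ≥1.0, platelets ≥75 × 10⁹/L).* It governs restarting after a hold, and it contains no hemoglobin value.
- *Table 4.* It is confined to non-hematologic toxicity. A separately reported Grade 3 or 4 infection would bring it into play. Fever with neutropenia and no such event would not.
- *Stopping rules (Section 5.1).* They "will trigger a hold on further patient enrollment for all dose cohorts", which concerns new patients and not the affected patient's dosing.

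After Cycle 1, nothing listed here turns the option to hold into a requirement for either event.

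**The case against.** The strongest reply is that nothing in the protocol tells anyone to dose through these events. Section 6 calls the tables guidelines and lets any dose be delayed for an adverse event. The Grade 3 ANC row tells the investigator to find and treat the cause, and the catch-all row expressly allows a hold. A competent investigator would stop the drug on the first day. That is right, and it limits the point to discretion versus obligation. It does not remove the point: for febrile neutropenia in this ANC range, the specific row still makes the hold the second step, two weeks on.

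A second reply is that the DLT definition ends at day 28 and covers only events at least possibly related to AC699. DLTs drive escalation, and a dose-modification table need not mirror them. This also stands. The DLT list is used here only as the protocol's own statement of how serious the events are. It does not show that the two sections contradict each other.

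Third, Cycle 1 is largely covered by the Section 6 rule and by the agreement that Section 5.1 asks of the Investigator, Medical Monitor and Sponsor before a patient with a DLT continues. This is accepted, and it is why the point is confined to later cycles.

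Three stronger readings may tempt a reader. One is that patients will receive 14 doses while febrile and neutropenic; that figure is only the row's ceiling. Another is that all febrile neutropenia is unprotected; with ANC <0.5 it falls in a row that requires a hold. The third is that the 3+3 decisions or the MTD are affected; the DLT count does not depend on Table 3. The documents support none of these.

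**Conclusion.** The point holds in a limited form. After Cycle 1, Table 3 lacks a mandatory immediate hold for febrile neutropenia at ANC 0.5 to <1.0 × 10⁹/L and for Grade 4 anemia. The counts above describe the table's layout and do not measure risk.

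The likely burden is unknown. The documents give no expected frequency for either event, and Section 1.2 reports nonclinical clinical-pathology effects that were non-adverse, reversible and seen in one species only. The events may therefore be uncommon.

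The conclusion rests on two readings: that the Grade 3 ANC row applies to febrile patients because it makes no exception for them, and that the catch-all label means what it says about life-threatening events. If Grade 4 anemia is instead read into the catch-all because that row covers Grade 3 and above, the hold is discretionary and the conclusion is the same. This is a modest safety correction that should be made at the next amendment.

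**What to change.** In Table 3:

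1. Limit the two-week Grade 3 ANC row to afebrile neutropenia.
2. Add a row for febrile neutropenia at any ANC <1.0 × 10⁹/L: hold at once until the fever has resolved and ANC is ≥1.0 × 10⁹/L, the table's existing re-treatment level. Where ANC was <0.5, keep the present Grade 4 restart rules.
3. Add a row for Grade 4 anemia or other life-threatening hematologic toxicity without its own row: hold at once until recovery to Grade 2 or better, as in the table's ANC and platelet rows, or to baseline. Leave the restart dose to the investigator and Medical Monitor.
4. Restrict the catch-all row to Grade 3 events that are not life-threatening.

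The Cycle 1 DLT rule in Section 6 stays as it is. A sentence saying that it takes precedence over Table 3 in Cycle 1 would only clarify.

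The change is two new rows and two edited labels, with no new assessments or data collection. The costs are a few more mandatory holds, including some for disease-related anemia, since the new rows (like the present ANC and platelet rows) carry no attribution limit, and less room for investigator judgment. A hold for treatment-related toxicity that lasts beyond 3 weeks would also meet footnote a, under which the patient is discontinued by default unless the treating physician and Medical Monitor agree otherwise. Setting anemia recovery at Grade 2, not Grade 1, makes that outcome less likely.

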6.2 Dose Modifications due to Non-Hematologic Toxicity

Dose modifications due to non-hematologic toxicities are shown in Table 4.

Table 4 Dose Modifications due to Grade 3 or 4 Non-Hematologic Toxicities

Toxicity Grade	AC699 Dose ^a	
Grade 3 (except nausea, vomiting, alopecia, diarrhea, rash, and fatigue)	Hold ^a until recovery to ≤ Grade 1 or baseline	
Toxicity resolves in ≤7 days	Resume at original dose	
Toxicity resolves >7 days and <3 weeks	Reduce by 1 dose level	
Toxicity does not resolve to ≤ Grade 1 or baseline within 3 weeks	Discontinue treatment. If in the patient's best interest, dose may be resumed at a lower dose only after discussion and agreement with Medical Monitor.	
Recurrence of the above same toxicity	Hold ^a until recovery to ≤ Grade 1 or baseline	
Toxicity resolves ≤7 days	Resume at original dose or reduce by 1 dose level at the Investigator's discretion ^b	
Toxicity resolves >7 days	Discontinue treatment. If in the patient's best interest, dose may be resumed at 1 reduced dose level only after discussion and agreement with Medical Monitor.	
Grade 4 (except asymptomatic electrolyte abnormalities that respond to treatment and resolve to ≤ Grade 2 within 72 hours, nausea, vomiting, alopecia, diarrhea, rash, and fatigue)	Discontinue treatment	
	Hold ^a	
Grade 4 asymptomatic electrolyte abnormalities that respond to treatment and resolve to ≤ Grade 2 within 72 hours	Once resolved as mentioned, treatment may continue at 1 reduced dose level at the Investigator's discretion and upon discussion with Medical Monitor	
Grade 3 or 4 nausea, vomiting diarrhea, rash and fatigue	Hold and institute maximum supportive treatment until recovery to \leq Grade 1, baseline or tolerable Grade 2	
Toxicity resolves ≤7 days	Resume at original dose	
Toxicity resolves >7 day and <3 weeks	Reduce by one dose level ^b	

CONFIDENTIAL

Study Drug: AC699 Sponsor/Development Innovations Study Numbers: AC699-001/BRE 401

Toxicity Grade	AC699 Dose ^a
Toxicity does not resolve to \leq Grade 1 or baseline, or tolerable Grade 2 by 3 weeks	Discontinue treatment. If in the patient's best interest, dose may be resumed at a lower dose only after discussion and agreement with Medical Monitor.
Recurrence of the above same toxicity	Hold and institute maximum supportive treatment until recovery to \leq Grade 1, baseline or tolerable Grade 2
Toxicity resolves ≤7 days	Resume at original dose or reduce by one dose level at the Investigator's discretion ^b
Toxicity resolves >7 days	Discontinue treatment. If in the patient's best interest, dose may be resumed at a lower dose only after discussion and agreement with Medical Monitor.

a AC699 should be held until toxicity resolves to ≤ Grade 1 or baseline. Any patients who develop irreversible Grade 3/4 non-hematologic toxicity that does not resolve to ≤ Grade 1 or baseline within 3 weeks after maximum supportive treatment should be removed from the study unless the treating physician and the Medical Monitor agree that continued treatment at lower doses is in the best interest of the patient.

6.2.1 Specific Recommendations for Liver Function Test Abnormalities

For patients with Grade 3 liver enzyme elevations (AST/ALT), AC699 should be held until the values recover to \leq Grade 1 or baseline. Patients with an elevation of AST/ALT \geq 3 × ULN in conjunction with a bilirubin \geq 2 × ULN may remain in the study if a correctable, non-drug related cause of the liver test evaluations can be documented; otherwise, the patient must be discontinued from the study.

7. STUDY ASSESSMENTS AND EVALUATIONS

7.1 Overview

All patients should visit the study center within the window of days specified within this protocol. The complete Schedule of Assessments for this study is presented at the beginning of this protocol (see the Schedule of Assessments). The key procedures required in this study include:

- Reporting of all AEs occurring after the ICF has been signed
- PK samples throughout the study
- Baseline and on-treatment blood biomarker assessments
- Tumor biopsy biomarker assessments (optional)
- Tumor assessments (based on CT/positron emission tomography [PET], bone scans, and/or magnetic resonance imaging [MRI] scan) according to RECIST Version 1.1 (see Appendix B).

CONFIDENTIAL

Study Drug: AC699 Sponsor/Development Innovations Study Numbers: AC699-001/BRE 401

^b No more than 2 dose reductions of AC699 are allowed unless the treating physician and the Medical Monitor agree that continued treatment at lower doses is in the best interest of the patient.

A cycle of treatment is scheduled to last 4 weeks (28 calendar days). Multiple procedures may be scheduled at the same time point relative to AC699 dosing. Priority should be given to PK collection at the time specified. Vital signs and ECG assessments should be performed prior to specimen collections or with proper time interval in between as to not artificially alter the vital signs collection.

7.2 Screening

At enrollment, each potential research patient will provide written informed consent ≤28 days prior to first dose of study drug administration and prior to starting any study-specific procedures. Upon signature of the ICF, patients will be assigned a unique subject number as enrollment (screening) occurs.

The screening assessments described in the Schedule of Assessments will be collected, reviewed, and determined to be acceptable by the site Principal Investigator or designee after obtaining informed consent prior to the first dose of study drug administration. Patients who do not meet all inclusion criteria, or who meet an exclusion criterion, may be rescreened once. Rescreening is at the discretion of the Investigator and the reason for rescreening should be discussed with the Sponsor. The Sponsor or designee will review results from the screening visit prior to enrollment to confirm patient selection for the study.

The following screening parameters should be recorded ≤28 days prior to first dose of study drug administration:

- ECHO (This test may be repeated as clinically indicated.) A MUGA scan maybe obtained in place of an ECHO to determine ejection fraction.
- Pre-treatment biopsy (optional)
- Tumor (radiographic) assessments
- Review patient menopausal status. Premenopausal or perimenopausal women must receive concurrent treatment with LHRH agonist and agree to use highly effective contraception as defined in Appendix C. Draw estradiol and FSH levels for participants who do not meet other definitions of postmenopausal as defined in the inclusion criteria, if indicated.
- HIV, HBV, and HCV testing

The following screening parameters should be recorded ≤7 days prior to first dose of study drug administration:

- Medical history and demographics
- Physical examination
- ECOG performance status
- Vital signs (including height and weight)
- Triplicate ECGs. The screening ECG should be assessed before other procedures and after the patient has rested for at least 3 minutes. Each recording should be separated by at least 30 seconds.

CONFIDENTIAL

Sponsor/Development Innovations Study Numbers: AC699-001/BRE 401

Final Protocol: 07 May 2024 Version 4.0

- Hematology (including absolute lymphocyte count [ALC], absolute neutrophil count [ANC], red blood cell count [RBC], reticulocytes, hemoglobin, hematocrit, 5-part differential, platelet counts, and prothrombin time [PT] / partial thromboplastin time [PTT] / international normalization ratio [INR])
- Biochemistry (sodium, potassium, phosphate, chloride, creatinine, total calcium, total CO₂ or venous bicarbonate [HCO₃], albumin, total protein, AST, ALT, ALP, bilirubin, lactate dehydrogenase [LDH], glucose, creatinine kinase [if CK is elevated, and elevation is clinically significant in the judgment of the Investigator, then CK-MB, troponin I, and myoglobin should be reactively tested, with further follow-up as clinically warranted], urea nitrogen, and uric acid)
- A serum pregnancy test is required for all women of childbearing potential (WOCBP). It is not required for post-menopausal women.
- Urinalysis

If these assessments are performed within 72 hours of first dose of study drug administration, they do not need to be repeated on Cycle 1 Day 1, with the exception of ECOG performance status, physical examination, vital signs, and triplicate ECGs. Tumor assessments (scans) should be performed ≤28 days prior to first dose of study drug administration.

Relevant concomitant diagnoses and/or therapies present at study entry and/or during screening that are relevant to the patient's safety during the study as judged by the Investigator will be recorded in the eCRF (see Section 5.4 for details on concomitant medications).

7.3 Assessments During Study Treatment

7.3.1 Cycle 1 (Days 1 and 15)

- Physical examination
- ECOG performance status
- Vital signs (including weight)
- Hematology (including ALC, ANC, RBC, reticulocytes, hemoglobin, hematocrit, 5-part differential, platelet counts, and PT/PTT/INR)
- Biochemistry (sodium, potassium, phosphate, chloride, creatinine, total calcium, total CO₂ or venous HCO₃, albumin, total protein, AST, ALT, ALP, total bilirubin, direct bilirubin, lactate dehydrogenase, glucose, CK [if CK is elevated and elevation is clinically significant in the judgment of the Investigator, then CK-MB, troponin I, and myoglobin should be reactively tested, with further follow-up as clinically warranted], urea nitrogen, and uric acid)
- Urinalysis

Study Drug: AC699

- Pharmacokinetics (See Appendix F):
 - OPK samples will be collected at pre-dose; at 1-, 2-, and 4-hours post-dose $(\pm 5 \text{ min})$; 6- and 8-hours post dose $(\pm 10 \text{ min})$; and 24 hours post-dose $(\pm 1 \text{ hour})$.

CONFIDENTIAL

Sponsor/Development Innovations Study Numbers: AC699-001/BRE 401

- o Triplicate ECGs will be conducted closely before each pre-dose 1-hour, 2-hour, 4-hour, and 6-hour post-dose PK sample collection, and after the patient has rested for 3 minutes. Each recording should be separated by at least 30 seconds.
- Biomarkers (circulating tumor [ctDNA] and circulating tumor cells [CTC]) Cycle 1 predose
- Review patient diary (Day 15 only)

